8.2.2.2. Proportions of subjects with HbA1c of < 7% over time

This endpoint will be analyzed using generalized estimating equation logistic regression. The treatment-by-visit interaction term will be removed if not significant. An unstructured correlation structure will be used (or autoregressive(1) if the model with the unstructured structure does not converge). Of interest is the difference between treatments across all post-baseline time points. Also, odds ratios will be estimated from the model with the corresponding p-values and their two-sided 95% CIs presented at each visit. The odds ratios of bexagliflozin group over the placebo group at each visit and across all post-baseline time points will be estimated from LS means based on the model with the corresponding p-values and their two-sided 95 % CIs presented. Sample SAS code will be provided in Appendix 1.

1007728

9. SAFETY

All analyses described in this section will be performed separately for each part of the study. The analysis population used for safety analyses will be the Safety Analysis Set. Safety data include AEs; physical examination results; vital signs, including blood pressures; ECG results; and clinical laboratory results, including serum chemistry, hematology, serum lipids, and urinalysis.

Observed data will be summarized by treatment group as counts and percentages for discrete variables and means, standard deviations, medians, inter-quartile range, minimum, and maximum for continuous variables. All subjects who are randomized and receive at least one dose of double-blind study medication will be included in the safety analysis. All safety data will be presented in by-subject listings and included in the clinical trial report.

9.1. EXTENT OF EXPOSURE

Study drug exposure will include:

- Treatment duration by treatment group
- Total dose received by treatment group

Treatment duration of tablets (in weeks) is calculated as (the date of the last dose of study drug - the date of the first dose of study drug + 1) / 7 and rounded to 1 decimal place.

The specific definitions of the first dose and last dose dates of study drug are given below:

- First dose date: The date of the first dose of study treatment during the double-blind treatment period obtained from the study drug exposure CRF.
- Last dose date: The date of the last dose of study medication in the 24 week treatment period for subjects who have completed the study or discontinued early. If the date of last dose is unknown, this date will be estimated using the last study drug return date, if available; otherwise, the date of the last completed visit will be used. Total dose received will be calculated as number of tablets dispensed number of tablets returned.

Summary statistics for treatment duration (in weeks) and total dose received, as well as a frequency summary of treatment duration categories (e.g., < 1, 1 - < 6 weeks), will be provided.

1007728

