5.3 Selection and Timing of Dose for Each Subject

Dosing with bexagliflozin tablets, 20 mg or placebo, will be based on randomized assignment. All study subjects will be instructed to self-administer tablets once daily with 250 mL of water in the morning prior to eating or drinking. There will be no change of dose during the 24-week treatment period.

On the day of each scheduled clinic visit, subjects must fast for approximately 10 hours prior to the collection of blood samples. On the day of each scheduled clinic visit, bexagliflozin tablets should be taken with water in the morning prior to eating or drinking (as above) and prior to the collection of blood samples. During the fasting period, only water will be permitted.

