5.9 Packaging and Labeling

Investigational product will be provided to the pharmacist or designated site personnel in bottles of 90 tablets enclosed with a child-resistant cap. Bottles of 15 placebo tablets will be provided for the 2-week run-in portion of the study. All investigational product supplies will be prepared and labeled according to the requirements of local laws and regulations and will be kept in a secure storage facility at controlled room temperature, 15 to 30 °C (59 to 86°F).

The pharmacist or designated site personnel will dispense the investigational products for each subject according to randomization assignment made in the Interactive Web Response System (IWRS). During the treatment period, subjects will be provided with an investigational product kit at randomization (Visit V6) and a new investigational product kit at 12 weeks (Visit V9). There will be no intra-subject dose escalation or back-titration.

Subjects who require rescue medication due to hyperglycemia will receive standard care for T2DM in addition to the investigational product.

There are two types of investigational product kits:

RUN-IN KIT

One run-in kit contains a bottle of 15 bexagliflozin tablets, placebo.

The label attached to each run-in kit will contain the protocol number, product identification, lot number, subject number, storage condition, sponsor's name and address, and the investigational drug caution statement.

INVESTIGATIONAL PRODUCT KIT

One investigational product kit contains a bottle of 90 bexagliflozin tablets, 20 mg or bexagliflozin tablets, placebo.

The label attached to each investigational product kit will contain the following information: the kit number, protocol number, product identification, blinded batch number, subject number, storage conditions, sponsor's name and address, investigator's name, and the investigational drug caution statement.

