6.4. ANALYSIS VISIT WINDOWS

Table 3 shows how data will be mapped to analysis visits prior to selection of records for analysis. All post-baseline visits, including unscheduled and early termination visits, will be mapped. After mapping the data to the analysis visits, the following rules will apply unless other handling is specified for a particular analysis.

- If multiple records are available within a single analysis visit window, the record closest to the planned assessment day will be selected for analysis.
- If 2 records are equidistant from the target day, then the later record will be selected.
- If a subject has no record in an analysis window, the subject will be considered missing at that visit.

1007728

Table 3 Analysis Visit Windows

Study Day Window	Scheduled day	Scheduled Visit/Week
Day 1 - 63	Day 42	Visit 8/Week 6
Day 64 - 105	Day 84	Visit 9/Week 12
Day 106 - 147	Day 126	Visit 10/Week 18
>= Day 148	Last Dose Date + 1	Visit 11/Week 24

^{*} Week 24 is the end of treatment visit for those subjects completing the study per protocol. For safety endpoint of lab, vital sign, and ECG, the first collection after assigned Week 24 and > 7 days from Week 24 visit will be considered as Week 26 visit.

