9.2. TREATMENT COMPLIANCE

Subjects will be provided with dosing instructions each time study medication is dispensed. Subjects will also be instructed to bring their medication with them to every visit. During the run-in period, subjects will be considered compliant in investigational product administration by missing no more than one dose of run-in medication. Subjects who are not compliant during the run-in period will be excluded from randomization.

At each visit the study staff will review the self-monitored blood glucose (SMBG) control diary, glucometer data and medication use with the subject and record the drug consumption in the CRF. Reasons for non-adherence will also be recorded in the protocol deviation log if applicable.

Compliance in the run-in and double-blind phase is calculated for as follows:

- Percent compliance = (number of tablets taken / number of tablets should have taken) x 100.
- Number of tablets taken = number of tablets dispensed number of tablets returned.
- Number of tablets should have taken = (number of tablets supposed to take in a day)
 x (number of exposure days).
- Number of exposure days = last dose date first dose date + 1.

If any of the bottles dispensed is not returned, it will not be possible to compute the compliance. In this case, the number of tablets taken and compliance will be considered as missing. Summary statistics for tablet compliance (%) will be provided by treatment group for the double-blind treatment period. A frequency summary of compliance will also be presented with the following categories: < 75%, 75-<100%, 100-120%, and > 120%.

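### For an unknown last dose date, SAP 9.1 lets the return of an earlier bottle override a later attended visit, and its total-dose formula is not reconciled with SAP 9.2

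*SAP*

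**What the plan says.** SAP 9.1 defines treatment duration in weeks as last dose date minus first dose date plus 1, divided by 7. For a last dose date that is not known, the rule reads: "this date will be estimated using the last study drug return date, if available; otherwise, the date of the last completed visit". The visit date is therefore a fallback only for subjects with no return date at all.

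Protocol 5.9 says that "subjects will be provided with an investigational product kit at randomization (Visit V6) and a new investigational product kit at 12 weeks (Visit V9"), and that "One investigational product kit contains a bottle of 90 bexagliflozin tablets, 20 mg" or placebo. Dosing is one tablet a day (Protocol 5.3).

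On quantity, SAP 9.1 states: "Total dose received will be calculated as number of tablets dispensed number of tablets returned", which is to be read as a subtraction. It has no rule for a bottle that never comes back. SAP 9.2 uses the same subtraction for tablets taken but adds: "If any of the bottles dispensed is not returned, it will not be possible to compute the compliance". In that case tablets taken and compliance are both set to missing.

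**The concern.** A return date is evidence of when a particular bottle left the subject's hands. Once a newer bottle has been dispensed, the return of the older one says nothing about when dosing stopped. The rule in 9.1 nevertheless ranks that date above a later visit attended while the subject held the newer bottle.

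The quantity rule errs in the opposite direction. For the same subject, duration could be understated while total dose is overstated. SAP 9.2 treats the identical quantity as unknowable. Exposure and compliance share Table 14.1.6 and Listing 16.2.5.2, so the inconsistency would be visible.

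At stake are the exposure summaries. The rates per 100 patient-years in SAP 9.3.3 could also be touched if their denominator is treatment duration, but the SAP does not define that denominator.

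**Working it through.** **Inputs**
- Kits: 90 tablets each, at V6 and V9 only (Protocol 5.9), so 2 × 90 = 180 dispensed.
- Dose: one tablet a day (Protocol 5.3).
- Scheduled days: V9 Day 84, V10 Day 126 (SAP 6.4, Table 3). Visit window ±3 days (SAP 3.9).
- Assumed: bottle 1 is handed back at V9, bottle 2 never comes back, no other return is logged, and the last dose date is unknown.

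**1. The plan's own figure.** Protocol 6.12 says one bottle covers 12 weeks. 12 × 7 = 84 tablets. If V9 is counted as Day 85 and falls 3 days late, 88 are needed. Both are within 90, so the figure reproduces, and a fully adherent subject still has a few tablets left at V9.

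**2. Duration for a subject who attends V10 and is then lost**
- Rule in 9.1: last dose date = V9, so 84 / 7 = 12.0 weeks.
- Last completed visit: 126 / 7 = 18.0 weeks.
- Difference: 126 − 84 = 42 days, and 42 / 126 = 33%.

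A subject in the same position who returned neither bottle has no return date. The fallback then applies and gives 18.0 weeks. Handing back bottle 1 thus lowers the credited exposure by six weeks.

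**3. Total dose for the same subject, by the literal 9.1 formula**
- Bottle 1 returned on Day 84 with 90 − 84 = 6 tablets: 180 − 6 = 174 tablets.
- V9 on Day 82 to Day 88 (Day 85 ± 3), full adherence: 8 to 2 tablets returned, so 172 to 178 received.
- Bottle 1 returned empty: 180.
- Against 84 days: 174 / 84 = 2.07 tablets a day on a once-daily regimen.
- Against 126 days: 174 / 126 = 1.38 a day. Correcting the date alone does not settle the dose.

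Under 9.2, tablets taken for this subject is missing.

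**4. Size across the trial**
- Planned patient-years: 210 × 168 / 365.25 = 96.6. If the 10% who terminate early leave on average halfway (assumed), the factor is 1 − 0.10 × 0.5 = 0.95, which gives about 92.
- Loss for k affected subjects: k × 42 / 365.25. For k = 2 this is 0.23 and for k = 8 it is 0.92 patient-years, or 0.3% to 1.0% of 92.
- The documents give no value for k. Eight is already 38% of the 21 early terminations expected (10% of 210).

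**The case against.** **The return of bottle 1 at V9 is not stated.** Protocol 5.9 says only that a new kit is provided then, and Protocol 5.10 leaves the return process to sponsor instructions. Under Protocol 5.11 subjects bring all product to every visit and remaining tablets are accounted for in the CRF. If those counts are logged as returns, a V10 attendee has a return date of about Day 126 and the duration error disappears. This stands, and it makes the duration point conditional. It does not defend the order of the rule, which gives the right answer only if sites record returns in that way.

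**The last dose date may seldom be unknown.** Drug consumption is recorded at each visit (SAP 9.2), and the tablet is taken on the morning of each clinic visit (Protocol 5.3). This also stands, and no frequency can be derived from the documents.

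**A reader might infer that the trial will report an impossible record of about two tablets a day.** The documents do not establish that. A programmer could apply the missing rule of 9.2 to the same quantity in 9.1, and the 207% would in any case never appear as compliance. What is supported is that 9.1 does not tell the programmer to do so.

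**A reader might also infer a threat to the primary endpoint**, because the Week 24 target in SAP Table 3 is "Last Dose Date + 1". A subject lost after V10 has no record on or after Day 148, so nothing changes. A V11 attendee would need an unknown last dose date despite dosing that morning, a return at V9 with none later, and an additional HbA1c between Day 148 and V11. Without that extra record, a target of Day 85 still selects V11 over V12, because V11 is nearer. No effect on the primary endpoint is shown.

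**Conclusion.** The point holds as a minor defect in two stated rules. First, the date order in 9.1 can understate exposure by about six weeks (12.0 against up to about 18.0) in a subject lost after V10, provided that bottle 1 was handed back at V9 and later tablet counts are not logged as returns. Eighteen weeks is itself an upper value, since such a subject may have stopped before V10. Second, 9.1 and 9.2 treat the same subtraction differently when a bottle is not returned: literally 172 to 180 tablets in one section, missing in the other. This second point does not depend on how visit counts are logged, only on bottle 2 not coming back.

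The consequence is confined to exposure summaries and listings for a few subjects. The ceiling of about 1% of patient-years rests on the assumed 2 to 8 subjects. An effect on adverse event rates is possible only if treatment duration is their denominator.

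**What to change.** In SAP 9.1, replace the rule for an unknown last dose date with:

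> If the date of last dose is unknown, use the return date of the last bottle dispensed; if that bottle was not returned, use the date of the last completed visit within the treatment period (through V11) at which the subject had not been recorded as having stopped study drug.

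Add:

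> Total dose received is missing if any dispensed bottle is not returned, as in 9.2.

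The cost is two sentences and a small program change before database lock. There are two drawbacks. A subject who stopped soon after V9 without this being recorded, but attended V10, could be credited with up to about 42 extra days. Total dose will be missing for a few subjects. The new wording leaves one feature of the present rule as it is: a last bottle handed back only at follow-up still gives a date about two weeks after the true last dose.

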9.2. TREATMENT COMPLIANCE

Subjects will be provided with dosing instructions each time study medication is dispensed. Subjects will also be instructed to bring their medication with them to every visit. During the run-in period, subjects will be considered compliant in investigational product administration by missing no more than one dose of run-in medication. Subjects who are not compliant during the run-in period will be excluded from randomization.

At each visit the study staff will review the self-monitored blood glucose (SMBG) control diary, glucometer data and medication use with the subject and record the drug consumption in the CRF. Reasons for non-adherence will also be recorded in the protocol deviation log if applicable.

Compliance in the run-in and double-blind phase is calculated for as follows:

- Percent compliance = (number of tablets taken / number of tablets should have taken) x 100.
- Number of tablets taken = number of tablets dispensed number of tablets returned.
- Number of tablets should have taken = (number of tablets supposed to take in a day)
 x (number of exposure days).
- Number of exposure days = last dose date first dose date + 1.

If any of the bottles dispensed is not returned, it will not be possible to compute the compliance. In this case, the number of tablets taken and compliance will be considered as missing. Summary statistics for tablet compliance (%) will be provided by treatment group for the double-blind treatment period. A frequency summary of compliance will also be presented with the following categories: < 75%, 75-<100%, 100-120%, and > 120%.

9.3. ADVERSE EVENTS

Adverse events will be collected and recorded from the time a subject signs the informed consent form (ICF) to the last scheduled contact. And new serious adverse events (SAE) reported by the subject to the investigator that occur after the last scheduled contact, and are determined by the investigator to be reasonably associated with the use of the investigational product, should be reported to the sponsor or designated personnel. This may include SAEs that are captured on follow-up telephone contact or at any other time point after the defined study period (i.e., up to last scheduled contact). The investigator should follow SAEs identified after the last scheduled contact until the events are resolved, or the subject is lost to follow-up. The investigator should continue to report any significant follow-up information to the sponsor until the event has been resolved. This study requires that subjects be actively monitored for SAEs for at least 4 weeks after the last treatment.

1007728

For all AEs, preferred AE terms and system organ class (SOC) will be coded using terminology from the Medical Dictionary for Regulatory Activities (MedDRA), version 19.0

A treatment-emergent adverse event (TEAE) is defined as an AE that begin after the first administration of double-blind study medication or existing AEs that worsen after the first dose of double-blind study medication. All reported AEs will be listed, but only TEAEs will be summarized in tables.

Drug-related AEs will be considered those to be possibly, probably and definitely related to bexagliflozin administration based on the investigators assessment.

Unless otherwise specified, AEs will be summarized by SOC and PT, with SOCs and PTs within SOCs presented in descending order of subject incidence.

9.3.1. Derived Data

AE onset day is calculated as (date of AE start - date of double-blind first dose + 1). The onset day will be missing if the start date is missing or partially missing.

9.3.2. Data Summarization

AE summary tables are listed below:

- An overall summary of the number and percentage of subjects reporting any TEAEs, serious TEAEs, treatment-related TEAEs, serious treatment-related TEAE, any TEAEs leading to treatment discontinuation, any TEAEs leading to subject discontinuation and TEAEs leading to death.
- TEAEs overall and by SOC and PT
- TEAEs by severity, overall and by SOC and PT
- Serious TEAEs, overall and by system organ class and preferred term
- TEAEs by relationship to study treatment, overall and by system organ class and preferred term
- TEAEs leading to treatment discontinuation, overall and by SOC and PT
- TEAEs leading to study discontinuation, overall and by SOC and PT
- Most common TEAEs. Most common TEAEs are defined as TEAEs that occur in
 5% of the subjects in either of the treatment groups.

1007728

For summary tables, subjects having more than 1 event with the same PT will be counted once for that term. Subjects having more than 1 event with the same SOC will be counted once for each event and once for that SOC. For tabulations by severity, only a subject's most severe event within the category (e.g. overall, SOC, PT) will be counted; similarly, for tabulations by relationship, only a subject's most related event within a category will be counted. The denominator for percentages will be the number of subjects in the Safety Analysis Set for the given treatment group (i.e., the N's for the columns).

Listings will be provided for all AEs and the following subsets:

- All TEAEs
- All TEAEs at least possibly related to bexagliflozin
- Serious AEs
- AEs leading to treatment discontinuation
- AEs leading to death.

Additional information will be collected for diabetic ketoacidosis (DKA). These data will be listed.

9.3.3. AE of Special Interest

AE of special interest include urinary tract infection (UTI), genital mycotic infection (GMI), diuretic effects, hepatotoxicity, cardiovascular events, hypoglycemia, fracture, malignancy, hypersensitivity reactions, hypotensive episodes, acid-base disorders, renal failure events, and amputations. These AEs of special interest, except for cardiovascular events and amputations, will be prospectively identified based on the MedDRA PTs in the AEs log by a medical expert prior to the data base lock and unblinding of the individual subject treatment assignment. The list of AEs of special interest will be confirmed in a peer review process. Cardiovascular events, hypoglycemia events by severity, and amputations will be summarized separately.

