2.3 Safety Objectives

- To compare the safety of bexagliflozin to the safety of placebo in subjects with T2DM
- To compare the effect of bexagliflozin to the effect of placebo on the incidence of adverse events (AE) of special interest. AEs of special interest include either upper or lower UTIs, GMI, hepatic toxicity, hypoglycemia, falls and fractures, cardiovascular events, malignancies, hypersensitivity reactions, hypotensive episodes, acid-base disorders, renal failure events and amputations.
- To contribute major adverse cardiovascular events (MACE+) to an eventual metaanalysis that is intended to exclude a hazard ratio of 1.8 or greater for subjects exposed to bexagliflozin compared to subjects exposed to placebo. MACE+ is defined as cardiovascular death, non-fatal myocardial infarction (MI), non-fatal stroke, or hospitalization for unstable angina.

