3.2.4 OTHER SAFETY MONITORING ACTIVITIES

The safety monitoring activities will include assessment of vital signs, physical examinations, urinalysis, blood chemistry, hematology, AEs, and concomitant medication (ConMed) use. The occurrence of blood, liver, or skin disorders will be monitored through laboratory testing and evaluation of adverse event documentation. Adverse events of special interest as defined in the statistical analysis plan will include any clinical signs and symptoms that indicate either upper or lower UTI, GMI, hepatic toxicity, hypoglycemia, falls and fractures, MACE+, malignancies, hypersensitivity reactions, hypotension episodes, acid-base disorders, and renal failure events. All such events must be appropriately documented within source documentation.

DATA AND SAFETY MONITORING BOARD (DSMB)

An independent DSMB will review unblinded safety information during the bexagliflozin development program. The safety review activities and potential risk benefit assessments utilized by the DSMB are defined in its charter.

MAJOR ADVERSE CARDIOVASCULAR EVENT ADJUDICATION

An independent cardiovascular endpoint committee (CEC) has been established to review, under blind, all potential cardiovascular events occurring during the study. The events of interest include cardiovascular mortality, myocardial infarction, stroke, hospitalization for acute coronary syndromes, urgent revascularization procedures, and other possible serious cardiovascular events. The adjudicated events will be documented and archived to allow a meta-analysis to be performed at a later time. Events occurring in this study will be classified as belonging to MACE+ or not. MACE+ is defined as cardiovascular death, non-fatal MI, non-fatal stroke, or hospitalization for unstable angina. No separate cardiovascular risk assessment will be performed based on events in the study population of the current protocol.

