3.3. SAFETY OBJECTIVES

- To compare the safety of bexagliflozin to the safety of placebo in subjects with T2DM.
- To compare the effect of bexagliflozin to the effect of placebo on the incidence of adverse events (AE) of special interest. AEs of special interest include either upper or lower UTIs, GMI, hepatic toxicity, hypoglycemia, falls and fractures, cardiovascular events, malignancies, hypersensitivity reactions, hypotensive episodes, acid-base disorders, renal failure events, and amputations.
- To contribute major adverse cardiovascular events (MACE+) to an eventual meta-analysis that is intended to exclude a hazard ratio of 1.8 or greater for subjects exposed to bexagliflozin compared to subjects exposed to placebo.

1007728

MACE+ is defined as cardiovascular death, non-fatal myocardial infarction (MI), non-fatal stroke, or hospitalization for unstable angina.

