9.3.3.1. AE of special interest identified by PTs

The number and percentage of subjects experiencing these TEAEs of special interest will be summarized for each treatment group by type of event. The incidence rate of AE of special interest per 100 patient years will also be summarized. Each category of events will be displayed in a separate listing.

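### Falls belong to the stated safety objective, but the operative lists of adverse events of special interest name fracture only, so the combined falls-and-fractures category would not be reported

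*SAP*

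**What the plan says.** The safety objective is to compare the arms on the incidence of adverse events of special interest. Protocol 2.3 spells these out: "AEs of special interest include either upper or lower UTIs, GMI, hepatic toxicity, hypoglycemia, falls and fractures, cardiovascular events", and further categories follow. SAP 3.3 repeats the list: "hepatic toxicity, hypoglycemia, falls and fractures, cardiovascular events, malignancies, hypersensitivity reactions, hypotensive episodes", and so on.

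Protocol 3.2.4 hands the definition to the SAP and says what it will contain: "Adverse events of special interest as defined in the statistical analysis plan will include any clinical signs and symptoms that indicate" a series of events, among them "hypoglycemia, falls and fractures, MACE+, malignancies, hypersensitivity reactions, hypotension episodes".

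The operative list is in SAP 9.3.3. After urinary tract and genital mycotic infections it names "diuretic effects, hepatotoxicity, cardiovascular events, hypoglycemia, fracture, malignancy, hypersensitivity reactions, hypotensive episodes, acid-base disorders, renal failure events, and amputations". Protocol 9.7.2 carries the same list, and the synopsis also names fractures without falls. Under SAP 9.3.3 a medical expert selects the preferred terms before database lock and unblinding, and a peer review confirms the list.

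SAP 9.3.3.1 gives the categories identified in this way a number and percentage of subjects by arm and an incidence rate per 100 patient-years. It adds: "Each category of events will be displayed in a separate listing". SAP 12 states that nothing has changed from the protocol's planned analysis.

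**The concern.** An objective that names an event category needs an analysis that reports that category. Here the objective and the monitoring section define the category as falls and fractures, while the sections that instruct the analysis define it as fracture. A fall without a fracture belongs to the first category and not to the second.

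The selection of terms is meant to be done blind. If the mismatch is noticed only after the codes are broken, a falls grouping would have to be built by people who can see the treatment assignments. That would be a post hoc grouping in a comparison the plan meant to protect by prior selection. The risk is conditional, because the conflict can still be resolved before lock.

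**Working it through.** No sample size, rate or error probability enters this point, and the plan gives no figure to reproduce. The check is a comparison of lists.

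**Step 1. Where falls appear.**

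| Place | Function | Entry |
|---|---|---|
| Protocol 2.3 | objective | falls and fractures |
| SAP 3.3 | objective | falls and fractures |
| Protocol 3.2.4 | says what the SAP definition will contain | falls and fractures |
| Protocol synopsis, Safety Assessments | summary | fractures |
| Protocol 9.7.2 | analysis | fracture |
| SAP 9.3.3 | analysis, term selection | fracture |
| SAP Listing 16.2.7.2.7 | output | fracture |

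Three places include falls and four do not. Every place that directs an analysis or an output is among the four. The split runs through the protocol itself: 2.3 and 3.2.4 on one side, the synopsis and 9.7.2 on the other.

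**Step 2. Objective against operative list.** The objective has 12 categories: urinary tract infection, genital mycotic infection, hepatic toxicity, hypoglycemia, falls and fractures, cardiovascular events, malignancy, hypersensitivity, hypotension, acid-base disorders, renal failure, amputation. SAP 9.3.3 has 13. It has all of these, with falls and fractures cut to fracture, plus diuretic effects (12 + 1 = 13). Falls are the only content of the objective missing from SAP 9.3.3.

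**Step 3. What is still planned for falls.** SAP 9.3.2 tabulates all treatment-emergent events by system organ class and preferred term, and also by severity, relationship, seriousness and discontinuation. A fall reported as an adverse event is counted by arm in Table 14.3.1.2 and appears in Listing 16.2.7.1. What is missing is the row in Table 14.3.1.10, the rate per 100 patient-years and a dedicated listing.

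**Step 4. Whether the combined category can be recovered from the general table.** It cannot. SAP 9.3.2 counts a subject once per preferred term. Suppose, in the simplest case of one term each, that *a* subjects in an arm have a fall term and *b* have a fracture term. The number with either lies between max(*a*, *b*), when the smaller group lies wholly inside the larger, and *a* + *b*, when no subject has both. The table gives *a* and *b* but not the overlap. The once-per-subject count that the objective calls for needs a derivation from subject-level data, and the plan does not specify one.

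**Step 5. Listings.** SAP 9.3.3 has 13 categories and the index has 12 category listings, 16.2.7.2.1 to 16.2.7.2.12, so 13 − 12 = 1 is missing. The index passes from hypersensitivity (.9) to acid-base disorders (.10). The missing one is hypotensive episodes.

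**The case against.** The strongest reply is that this is loose drafting with little effect. The special-interest lists vary elsewhere too: Protocol 3.2.4 omits amputations and diuretic effects. SAP 9.3.3 introduces its list with an inclusive verb, so the expert could add fall terms while still blinded, and the peer review could catch the gap. Falls are counted by arm in any case. The rate adds little: if all planned subjects complete 24 weeks, exposure is about 140 × 24/52 = 64.6 and 70 × 24/52 = 32.3 patient-years, and with near-uniform follow-up a rate says much the same as a percentage.

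Most of this stands, and it limits the size of the point. It does not remove the point. The expert may add falls, but nothing in SAP 9.3.3 tells the expert to, and the listing index contains fracture alone. The general tables do not yield the combined count.

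Four stronger readings are tempting, and the documents do not support them.

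- *Falls have no planned analysis.* They do, as preferred terms in the general tables and in the all-event listing. Nor do the documents show that falls would be scattered over several terms.
- *The SAP departed from the protocol by dropping falls.* SAP 9.3.3 follows Protocol 9.7.2, so the conflict begins inside the protocol. The statement in SAP 12 is true against 9.7.2 and untrue against 2.3 and 3.2.4.
- *The hypotension part of the objective is also unanswered.* Hypotensive episodes are in SAP 9.3.3 and so get a count, percentage and rate in Table 14.3.1.10. Only the index line is missing.
- *Falls matter here because the trial tests blood-pressure lowering.* The documents never make that link; they pair falls with fractures.

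**Conclusion.** The point holds as an inconsistency with a limited consequence. Of the objective's 12 categories, one would be reported for fractures alone: no special-interest count, no rate per 100 patient-years and no dedicated listing for falls, and no once-per-subject figure for falls and fractures together. Efficacy conclusions, alpha, power and data collection are not affected.

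This rests on two assumptions. The first is that the analysis follows SAP 9.3.3 as written, which is reasonable because Protocol 9.1 makes the SAP the final plan. The second is that the expert's term list, which is not among the documents, keeps to the named categories. If that list already includes falls, the remaining defect is wording. The texts do not show whether falls were left out on purpose. SAP 3.3 still carries them, so deliberate removal cannot be presumed.

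The missing hypotensive-episodes listing is a clerical correction and would not merit a point of its own.

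**What to change.** Before database lock and unblinding:

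1. In SAP 9.3.3 replace fracture with falls and fractures, counted once per subject, with falls and fractures also shown as separate rows. Fix the preferred terms for each while blinded.
2. Carry the category and its two rows into Table 14.3.1.10 with number, percentage and rate per 100 patient-years, and cover falls in the 16.2.7.2 listings.
3. Align Protocol 9.7.2 and the synopsis.
4. Add the hypotensive-episodes listing to the 16.2.7.2 series.

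If the sponsor meant to leave falls out, items 1 to 3 are replaced by amending the objectives in Protocol 2.3 and SAP 3.3 and the text of Protocol 3.2.4, and recording the change in SAP 12. Either route resolves the conflict.

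The first route costs wording edits, added rows in one table and two listings, all from adverse event data already collected. The second costs wording only, plus item 4.
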